## 4.2. Purpose

Obtain clinical data in Chinese patients to support product registration of the MiniMed™ 670G system with the National Medical Product Administration (NMPA) in China. The results from the study will be submitted to the NMPA for product registration.

## 5. Objectives and Endpoints

### 5.1. Objectives

#### 5.1.1. Primary Objective(s)

To evaluate the safety, effectiveness and usability of the Medtronic MiniMed™ 670G system in Chinese patients with type 1 diabetes.

*Medtronic Confidential*

## 5.2. Endpoints

### 5.2.1. Primary Endpoint

Time in target range (% of SG): 70 mg/dL (3.9 mmol/L) ≤ SG ≤ 180 mg/dL (10 mmol/L)

The overall mean change in % of time in target range from run-in period to study period will be estimated and compared by a simple superiority paired test and a significance level of 0.025 (one-sided).

### 5.2.2. Secondary Endpoints

- Time in hypoglycemic range (% of SG): SG < 70 mg/dL (3.9 mmol/L), 60 mg/dL (3.3 mmol/L) and 54 mg/dL (3.0 mmol/L)
- Time in hyperglycemic range: SG > 180 mg/dL (10 mmol/L), 250 mg/dL (13.9 mmol/L) and 350 mg/dL (19.4 mmol/L)
- Glucose variation: the standard deviation (SD) of SG and the glucose coefficient of variation (CV)
- Change of Total Daily Dose (TDD) of insulin and weight from baseline to EOS
- Time spent in Auto Mode (HCL) versus time spent in Manual Mode (open loop)
- Stratified by HbA1c Ranges (< 7%, 7 – 7.5%, 7.5 – 8%, > 8%)
  - Time in target range (% of SG): 70 mg/dL (3.9 mmol/L) ≤ SG ≤ 180 mg/dL (10 mmol/L)
  - Time in hypoglycemic range (% of SG): SG < 70 mg/dL (3.9 mmol/L), 60 mg/dL (3.3 mmol/L) and 54 mg/dL (3.0 mmol/L)
  - Time in hyperglycemic range: SG > 180 mg/dL (10 mmol/L), 250 mg/dL (13.9 mmol/L) and 350 mg/dL (19.4 mmol/L)

### 5.2.3. Safety

All adverse events will be collected from enrollment (i.e., time of consent) to study end including but not limited to:

- Serious Adverse Events (SAE)
- Serious Adverse Device Events (SADE)
- Unanticipated Adverse Device Effects (UADE)
- Incidence of Severe Hypoglycemia
- Incidence of Severe Hyperglycemia
- Incidence of DKA

**5.2.4. Device Deficiencies**

Descriptive summary will be used to characterize device deficiencies, which will be collected from enrollment (i.e., time of consent) to study end.

**5.2.5. Subject Feedback**

Descriptive summary will be used to characterize study questionnaire(s) results.

## 6. Study Design

This study is a multi-center, single arm study in insulin-requiring subjects with type 1 diabetes who are 14 years of age and older. The run-in period will be approximately up to 35 days long, followed by a study period that will be approximately up to 33 days in duration.

The study is anticipated to last no longer than 13 months from investigational center initiation to completion of all data entry and monitoring procedures. The study will target approximately 5 months to complete subject enrollment. Subjects can expect to participate for approximately 2-3 months including the run-in and study periods.

A total of up to 75 subjects (aged 14-75) will be enrolled at a minimum 2 investigational centers and up to 6 investigational centers (hospitals) in China to have at least 50 subjects who complete the study.

### Overview of the Run-in and Study Periods:

#### **Run-in Period :**

After enrollment and passing Screening requirements, subjects will be trained on pump use as well as the use of Continuous Glucose Monitoring (CGM) with transmitters and sensors.

The run-in period will be used to allow subjects to become familiar with new study devices. During the run-in period study subjects will be using the Study Pump (MiniMed™ 670G) and CGM with only the Sensor Augmented Pump (SAP) function activated (i.e. SmartGuard™ features such as Suspend on Low and Suspend before Low will remain turned OFF).

All subjects will be trained on the study devices and diabetes management principles, such as the treatment of hyperglycemia and hypoglycemia. A training checklist consisting of review of the MiniMed™ 670G system features will be completed and collected for each subject to ensure competency. In addition, there will be training regarding access to oral glucose, oral carbohydrates or glucagon in case of hypoglycemia.

For study purposes, subjects will be instructed to perform SMBG if they are experiencing a severe hypoglycemic event, severe hyperglycemic event or Diabetic Ketoacidosis (DKA). As a precaution, subjects will be told that they should keep their own insulin pump supplies in a safe place and to have back up supplies on hand (such as insulin and syringe) in the event they are asked to revert back to their own therapy during the study or experience study pump issues (i.e. infusion set occlusion with high glucose).

Subjects will be instructed to insert glucose sensors only in the locations that are specified in the User Guide materials. Reminders will be given to subjects at each office visit. Information about sensor insertions will be collected on an electronic Case Report Form (eCRF) in the study database, i.e. insertion location.

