#### *Study-specific inclusion criteria*

3. Subject is willing to perform  $\geq$  4 finger stick BG measurements daily.
4. Subject is willing to perform required sensor calibrations.
5. Subject is willing to wear the system continuously throughout the study.
6. Subject must have a minimum daily insulin requirement (Total Daily Dose) of greater than or equal to 8 units.
7. Subject has a Glycosylated hemoglobin (HbA1c) less than 10% (as processed by the investigational center lab or their contracted Local Lab) at time of Screening visit.
8. Subject has thyroid-stimulating hormone (TSH) in the normal range OR if the TSH is out of normal reference range the Free T3 is below or within the lab's reference range and Free T4 is within the normal reference range. Prior labs in the last 6 months are sufficient.
9. Subject has been on pump therapy for greater than 6 months prior to screening (with or without CGM experience).
10. Subject is willing to upload data from the study pump and meter at home.
11. If subject has celiac disease, it has been adequately treated as determined by the investigator.
12. Subject has been taking and is willing to take one of the following insulins throughout the course of the study:
  - o Humalog™\* (insulin lispro injection)
  - o NovoLog™\* (insulin aspart)
13. Subject must be able to carbohydrate count or willing to learn how to carbohydrate count for the study.

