**SmartGuard™ features should not be activated**
- Visit 3: Start CGM 0-7 days after Visit 2
  - Subjects who are using pump **without** CGM at Screening:
    - Start CGM, provide CGM Training
      - Recommend that this visit take place 5-7 days after Visit 2
      - Start CGM run-in (2 weeks)
      - Install Mobile App to Smartphone (if applicable)
      - System is set Manual Mode (Sensor Augmented Pump only):  

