# CIP329 Clinical Investigation Plan

10939060DOC

Version C

Page 50 of 99

Medtronic

	Run-in Period				Study Period				
	Visit 1 (O)	Visit 2 (O)	Visit 3 (O)	Visit 4 (O)	Visit 5,6 and 7 (O/T)	Visit 8 and 9 (O/T)	Visit 10 (O)	Visit 11 (O)	Visit 12 (O)
O= Office T= Telephone									
Upload the study pump during office visit (as applicable)		x	x	x	x	x	x	x	x
Enter eCRFs into the study database as appropriate	x	x	x	x	x	x	x	x	x
Collect study devices from subjects upon exit from study									x
Things to do (General Instructions/Training/Review)									
Train subjects on CareLink™ - Refer to Subject CareLink™ Uploading Instructions		x							
Instruct subjects on carbohydrate counting since subjects will need to carbohydrate count in order to use the study device		x	As needed	As needed	As needed	As needed	As needed	As needed	
Print and review CareLink™ Reports				x	x	x	x	x	x
Review surveillance report in Medtronic Box and recommend to review with subjects as necessary							x	x	x
Train subjects on sensor guidelines:									

 
Self-insert Guardian Sensor (3) per user guide and connect to Guardian Link (3) Transmitter
 
Sensor must be calibrated to ensure correct operation.
 
If there are any calibration problems with the sensor, the sensor may be replaced to ensure correct operation.
 
The investigator or qualified research staff will provide recommendations whether or not the SG low and high alerts should be turned on or off and, if they are turned on, at which threshold they should be set.
 
Subjects, with assistance from their parent(s)/guardian(s) where applicable, should replace the sensor after 7 days of use or as events dictate throughout the course of the study.
 
	x (as applicable)	x							

*Medtronic Confidential*

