#### **7.1.3 Analysis Sets**

- Intention to Treat (ITT) Population  
The Intention to Treat (ITT) population will include all subjects who start the study period.
- Per Protocol (PP) Population  
The Per Protocol (PP) population will include all subjects who complete the study period and stay in Auto Mode  $\geq 80\%$  of study period and have no major deviations (e.g. protocol violation in eligibility).
- Efficacy Population  
The primary analysis will be performed on the ITT population. Sensitivity analysis will be performed on PP population.
- Safety Population  
The Safety Population will include all enrolled subjects.

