## 7.9 Evaluation of Objectives

### 7.9.1 Primary Endpoints

Time in target range (% of SG): 70 mg/dL (3.9 mmol/L) ≤ SG ≤ 180 mg/dL (10 mmol/L)

The overall mean change in % of time in target range from run-in period to study period will be estimated and compared by a simple superiority paired test and a significance level of 0.025 (one-sided).

$H_0: \mu \leq 0\%$

$H_a: \mu > 0\%$

Where  $\mu$  is the mean of change in % of time in target range (1-month - baseline). The null hypothesis will be rejected if the one-sided 97.5% lower confidence limit of the mean change in % of time in target range is greater than 0%.

- Pass/Fail Criteria

The study pass/fail criteria is based on statistical hypothesis of the primary endpoint. The study will be considered as success when the evaluation criteria meets the predefined threshold.

- Justification for Exclusion of Particular Information from the testing of the Hypothesis

Not Applicable.

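### Does the plan need a late run-in baseline or weekly TIR table because the run-in is also the device-learning phase?

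*Protocol*

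**What the plan says.** Protocol Section 6 sets the design: "This study is a multi-center, single arm study in insulin-requiring subjects with type 1 diabetes". Under its Run-in Period heading it adds: "The run-in period will be used to allow subjects to become familiar with new study devices". SAP 7.9.1 makes that period the comparator: "The overall mean change in % of time in target range from run-in period to study period will be estimated". Success requires a one-sided 97.5% lower confidence limit above zero (Protocol 14.6.1 gives the same rule). The one named sensitivity analysis is in SAP 7.1.3: "Sensitivity analysis will be performed on PP population".

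On who is learning what, Protocol 8.3 requires more than six months of pump therapy but not CGM experience. It also admits beginners at carbohydrate counting: "Subject must be able to carbohydrate count or willing to learn how to carbohydrate count for the study". Table 3 places the teaching at Visit 2: "Instruct subjects on carbohydrate counting since subjects will need to carbohydrate count in order to use the study device". For subjects without CGM at Screening, Section 9.1 says of Visit 3, when their CGM starts: "Recommend that this visit take place 5-7 days after Visit 2". Subjects already on CGM may combine Visits 2 and 3. Auto Mode starts at Visit 4, which is 14 to 21 days after Visit 3, and is followed by five daily contacts (Visits 5 to 9) at which settings are adjusted as needed.

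**The concern.** With no control arm, the run-in is the only thing the Auto Mode period is compared with, and it doubles as a training phase. Subjects new to CGM or to carbohydrate counting could have lower TIR in their first days and improve before Auto Mode is switched on. That would lower the baseline, and against a 0% threshold each point of shortfall counts towards passing.

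No planned analysis would reveal it. The per-protocol analysis changes the subjects and keeps the baseline. The HbA1c strata use the same run-in and study periods. Glycated albumin is drawn at Visits 1 and 12, so its change spans run-in and Auto Mode together. The sensor data needed for a check are already stored by the pump, so a baseline from day 8 of CGM wear and a table of TIR by run-in week look like cheap safeguards. At stake is how much of a positive result can be credited to Auto Mode.

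**Working it through.** **Inputs.** From SAP 6: expected change 5.3 points, SD 13.0, n = 50, one-sided alpha 0.025. From Protocol 9.1: CGM run-in T = 14 to 21 days; study period 30 days (27 to 33). From Protocol 4.1.2: TIR rose from 60.4% to 67.2% in adolescents and from 68.8% to 73.8% in adults. Assumed, because the documents give no values: a first-week shortfall s; a within-subject daily TIR SD w of 10, 15 or 20 points; a day-to-day correlation of 0 or 0.5 (first-order autoregressive).

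**1. The plan's own figures.** Half-width = t × SD/√n = 2.0096 × 13.0/√50 = 3.69 points. Noncentrality = 5.3 × √50/13.0 = 2.88, which gives power 80.7%, in line with the stated figure of more than 80%. The effect also reproduces: weighting the adolescent change (6.8) and adult change (5.0) by 1:5 gives (6.8 + 5 × 5.0)/6 = 5.3. So the planning value is itself a run-in-to-study contrast from a trial with the same kind of run-in.

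**2. What a first-week shortfall would do.** If the first 7 days lie s points below the rest, the full baseline falls by s × 7/T.

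| s (assumed) | T = 14 | T = 21 |
|---|---|---|
| 2 points | 1.0 (19% of 5.3) | 0.67 (13%) |
| 4 points | 2.0 (38%) | 1.33 (25%) |

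If Auto Mode had no effect at all, a baseline lowered by 1.0 point would raise the chance of passing at n = 50 from 2.5% to 7.7%, and one lowered by 2.0 points would raise it to 18.6%. A first week above the rest would act the other way.

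**3. Could a day-8 baseline detect it?** The shift between the two estimates is the late-window mean minus the full-window mean. With independent days its variance per subject is w² × (1/(T − 7) − 1/T). For T = 14 and w = 10 this is 100/14 = 7.14, so the half-width is 2.0096 × √(7.14/50) = 0.76.

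| Setting | w = 10 | w = 15 | w = 20 |
|---|---|---|---|
| T = 14, correlation 0 | 0.76 | 1.14 | 1.52 |
| T = 14, correlation 0.5 | 1.11 | 1.67 | 2.23 |
| T = 21, correlation 0 | 0.44 | 0.66 | 0.88 |

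At T = 14 the half-width exceeds the 1.0-point shift in five of six cells. A 2.0-point shift exceeds the half-width in five of six. At T = 21 with independent days, the 0.67-point shift is larger than the half-width in two of three cells, in one of them barely. Correlation is plausible: a seven-day late window may rest on a single sensor, and Protocol 9.6.3 notes that calibration bias carries forward.

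**4. Cost in precision.** The SD of the change becomes √(13.0² + Var(late mean) − Var(full mean)). At T = 14 with independent days it is 13.27, 13.60 and 14.06, giving power of 79.0%, 77.0% and 74.3% at 5.3 points. With correlation 0.5 and w = 20 it is 15.18 and 67.7%.

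**5. One-sided trimming.** The day-8 analysis drops start-up days from the run-in but keeps those of Auto Mode, when settings are being adjusted. Suppose, for illustration, that each period has a first-week shortfall of 2 points. The study mean then falls by 2 × 7/30 = 0.47. The full-baseline estimate is off by 1.0 − 0.47 = +0.53 at T = 14, or 0.67 − 0.47 = +0.20 at T = 21. The day-8 estimate is off by −0.47 in both. The error changes sign, is barely smaller at 14 days, and is larger at 21.

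**The case for a change.** The best case for acting is that the gap is real and closing it is nearly free. The run-in is the sole comparator in a registration trial, no analysis varies the baseline window, and a cut-off chosen after the data are seen would carry less weight than one fixed beforehand. The 5-7 day gap is pump-only time, so it cannot absorb learning to use CGM. Nor does agreement with the earlier trial show that the contrast is free of drift, since that trial's run-in was also for learning the devices.

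Much of this stands as description: the check is absent, and CGM learning can fall inside the baseline. It does not show that the plan is wrong. The subjects with no gap are those already using CGM, who have least to learn about it; all subjects have more than six months on a pump; and carbohydrate counting is taught at Visit 2. What remains is mainly CGM learning in subjects without CGM at Screening, whose share the documents do not give. The raised pass probabilities need both an assumed drift and a zero Auto Mode effect, and the proposed analysis would not alter them.

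A weekly TIR table covering both periods is harmless and can be produced descriptively from stored data without amending the plan. The exact days that form the baseline are a separate wording matter and say nothing about learning bias.

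**Conclusion.** No change to the plan. Using the run-in as baseline in a single-arm study is an open trade-off, and the planning effect of 5.3 points rests on the same contrast. The documents contain no evidence that TIR drifts within the run-in, in either direction. For the shortfalls assumed here (2 to 4 points in week one) the estimate would move by 0.67 to 2.0 points. The suggested late baseline would resolve the upper end of that range better than the lower, could not separate the Auto Mode effect from other time trends, and would be lopsided because it trims only one side. The primary test, its 3.69-point half-width, its 80.7% power and its pass/fail rule would be the same with or without it. The precision figures rest on the assumed daily SDs and correlations; differences between subjects in learning would widen the half-widths further.

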#### **Study Period :**

---

*Medtronic Confidential*

The study period begins at Visit 4 in which subjects will begin using Auto Mode. The subject will have follow up visits after Auto Mode has been turned on to adjust insulin pump settings and then continue wearing the study devices until the end of the study period.

### Manual Mode Settings

- High glucose alert limit recommend to be set at 300 mg/dL (16.7 mmol/L)
  - Alert Setting Options may be set per investigator discretion
- Low glucose alert limit recommend to be set at 70 mg/dL (3.9 mmol/L)
  - Subjects will be instructed to follow up with an SMBG confirmatory measurement when receiving a low alert
  - Alert Setting Options may be set per investigator discretion
- Predictive alerts and rate of change alerts are optional
- Consider setting the glucose target in the bolus wizard calculator to the same target as the Auto Mode (HCL algorithm), i.e. 120 mg/dL (6.7 mmol/L) or higher, based on investigator discretion.

### Settings for Auto Mode:

- Auto Mode (HCL) basal rate target for the closed loop algorithm is factory set at 120 mg/dL (6.7 mmol/L)
- Auto Mode correction target is factory set at 150 mg/dL (8.3 mmol/L)
- The Temp target setting in the pump may be used when subject exercises. Temp Target Threshold is set to 150 mg/dL (8.3 mmol/L)
- Alarms that are fixed into system:
  - When SG at or below 50 mg/dL (2.8 mmol/L)
  - When SG at or above 300 mg/dL (16.7 mmol/L) for one hour
  - When SG at or above 250 mg/dL (13.9 mmol/L) for 3 hours
- High glucose alert limit (i.e. the setting for a high glucose alert threshold based on sensor reading) is recommended to be set at 300 mg/dL (16.7 mmol/L)
  - Alert setting options may be set per investigator discretion
- Low glucose alert limit (i.e. the setting for a low glucose alert threshold based on sensor reading) is recommended to be set at 70 mg/dL (3.9 mmol/L)
- Alert setting options may be set per investigator discretion
- Subjects will be instructed to follow up with an SMBG confirmatory measurement when receiving a low alert
- Insulin carbohydrate ratios may be adjusted throughout study.
- Active insulin time may also be adjusted.

### Blood Glucose Monitoring Method:

- Accu-Chek™\* Guide Link Study Meter

### **SMBG recommendations:**

Subjects will be instructed to check their blood glucose at least 4-6 times per day and also before driving (as applicable) for diabetes self-management (SMBG), using the supplied Study Meter according to the

user guide. Occasionally, subjects may receive a notification if the pump needs a blood glucose (BG) measurement to enter or to stay in Auto Mode.

## **6.1. Duration**

The study is anticipated to last no longer than 13 months from investigational center initiation to completion of all data entry and monitoring procedures. The study will target 5 months to complete subject enrollment. Subjects can expect to participate for approximately 2-3 months including the run-in and study periods.

## **6.2. Rationale**

Although the performance and safety of the MiniMed™ 670G System has already been studied in subjects in the United States, an evaluation involving Chinese subjects is required to support NMPA approval of the system.

---

*Medtronic Confidential*

## 7. Product Description

### 7.1. Intended Population

The Chinese population of subjects with type 1 diabetes will be studied. The study population will have a large range for duration of diabetes and glycemic control, as measured by HbA1c.

### 7.2. General Overview of MiniMed 670G System Components and Consumables

**Table 1. MiniMed™ 670G Insulin System Components and consumable materials**

Device name	MDT Model number/ part number	China
MiniMed™ 670G Insulin Pump	MMT-1883	Investigational
Guardian™ Sensor (3)	MMT-7020	Investigational
Guardian™ Link (3) Transmitter	MMT-7911	Investigational
One-press Serter	MMT-7512	Investigational
Charger	MMT-7715	Investigational
Tester	MMT-7736L	Investigational
Blue adapter	ACC-1003910	Investigational
MiniMed Mobile Application	MMT-6101/6102	Investigational
CareLink™ For Clinical Research Software	MMT-7338	Non-investigational
FreeStyle Optium Neo Ketone Meter		Non-Investigational
Accu-Chek™* Guide Link Study Meter	MTR114	Investigational

*Medtronic Confidential*

## 7.3. Investigational Devices

The investigational devices used in the study will be described in this section. Instructions for intended use, including indications, contraindications, and precautions of the components used in this study, are provided in their respective user guides/instructions for use (IFU).

### 7.3.1. MiniMed™ 670G Insulin Pump

The MiniMed™ 670G Insulin Pump, version 5.2, is capable of continuous insulin delivery, at set and variable rates, for the management of diabetes mellitus in persons requiring insulin. When used with the CGM components (Guardian™ Sensor (3), Guardian™ Link (3) Transmitter), the pump system is capable of continuous or periodic monitoring of glucose levels in the interstitial fluid under the skin and detection of possible low or high blood glucose episodes. The pump also displays SG values, storing this data so that it can be retrospectively analyzed to track patterns and improve diabetes management.

The MiniMed™ 670G Insulin Pump also includes the closed loop (CL) algorithm as part of the SmartGuard™ collection of features that may be enabled by the user. SmartGuard™ is comprised of Manual Mode Low Management, which includes the Suspend on low feature (suspends insulin delivery when a pre-set low SG threshold is reached), the Suspend before low feature (enables insulin to suspend 30 minutes before a pre-set low SG threshold is reached) and Auto Mode (hybrid closed loop) feature. The Auto Mode and Manual Mode Low Management features will not be active at the same time.

The pump may also be used as a simple pump without CGM or as a sensor augmented pump (SAP) without the SmartGuard™ features.

When Auto Mode is enabled on the MiniMed™ 670G insulin pump, the SG values received from the Guardian™ Link (3) Transmitter by the insulin pump will be used to automatically calculate the insulin dose. It will then deliver insulin to the patient, at five-minute intervals, to achieve glycemic control.

With the HCL system Auto Mode, subjects must still deliver bolus insulin for meals and corrections to the target SG level, as calculated by the insulin to carbohydrate ratio. This ratio is determined by the HCP/patient. In addition, the setting for active insulin must be programmed. Basal rates are set for period of open loop therapy.

When Auto Mode is not enabled, the user may enable the Low Management feature. Here, basal rate delivery will be suspended either when the SG reached a programmed low threshold (Suspend on Low) or before the SG value has reached the programmed low threshold (Suspend before Low).

The MiniMed™ 670G Insulin Pump contains Bluetooth® Low Energy RF communication, which allows for connectivity to patients' smartphones, CGM transmitter and the blood glucose meter.

